### Primary Outcomes

1. RV-induced expression of IL-25 mRNA transcripts in the asthma and AR cohorts versus healthy controls as determined in nasal scraping samples obtained on days 3 and 4 (compared to day 0) as determined by qPCR.
2. RV-induced lower respiratory symptoms in the asthma cohort versus AR and healthy control as determined using modified Jackson scores (1) that will include cough, chest tightness, wheezing, and shortness of breath as well as via the asthma control test (ACT).
3. Severity of infection in the asthma and AR cohorts versus healthy controls as quantified by viral load present in nasal secretion samples as determined by qPCR performed on days 1, 2, 3, 4, 7

### 3.2. Secondary Outcomes

1. IL-25 transcript expression in nasal scraping samples obtained on days 1, 2, and 7 (as compared to day 0).
2. Expression by nasal epithelial cells of a type 2 cytokine-inducing profile will be determined by also evaluating the time course of IL-33 and TSLP transcript expression by qPCR on nasal scraping samples obtained on days 0, 1, 2, 3, 4 and 7.
3. Expression of this type 2 cytokine-inducing profile will be corroborated by evaluating IL-25, IL-33, and TSLP protein expression by EIA on nasal secretion samples obtained via immunosorbent sponge.
4. Airway inflammation will be determined as increases in circulating absolute eosinophil counts, increased FeNO, and as changes in methacholine PD20.
5. Severity of RV infection will be corroborated as increases in upper respiratory symptoms using modified Jackson scores (1). This scoring system includes sneezing, nasal discharge, nasal obstruction, sore throat, headache, malaise, and chills.
6. Severity of RV infection will be correlated with decreased innate immunity as assessed as reduced IFN- $\alpha$ , - $\beta$ , - $\lambda$ , and IL-15 measured as qPCR of nasal scrapings and as enzyme immunoassays (EIAs) of nasal secretions (sponge-derived samples).

### 3.3. Exploratory Outcomes

1. Commercial EIAs for IL-33 and TSLP have been problematic and, additionally, IL-33 needs to be activated and, therefore, measuring full length IL-33 (or IL-33 transcripts) will not necessarily reflect biological activity. We therefore propose to complement these assays with functional studies demonstrating the ability of nasal secretions to support Th2 immune deviation in an ongoing immune response. For these studies we will investigate a non-specific pan-activating T cell signal ( $\alpha$ CD3/  $\alpha$ CD28 beads) and a universal antigen (tetanus) that consistently expand both Th1 and Th2 lymphocytes. These studies will demonstrate a Th2 immune deviating “milieu” but cannot address the specific cytokine responsible. However, these approaches permit the use of individual or combinations of neutralizing antibodies (and/or in the case of IL-33, blocking anti-ST2 antibody) that will allow us to identify the specific cytokine (or combinations) driving Th2 immune deviation.
2. Epigenetic Modification of the IL-25, IL-33, and TSLP genes will be assessed on nasal epithelial cell at baseline (day -28) using bisulphite modification/methylation-specific PCR and changes in histone acetylation patterns.
3. Nasal biopsies will be performed at day 4 dpi. Most (>90%) virions remain intracellular and, as such, nasal secretions do not accurately reflect the extent of viral infection. More importantly, nasal washes do not accurately sample the primary site of infection (the adenoids). Nor do washes give information regarding the diffuseness or associated cytopathological response of the infection, specifically whether cell death is apoptotic (and, as such, anti-inflammatory with IL-10, TGF- $\beta$ , and PgE2 release) or necrotic (and, as such, pro-inflammatory with IL33 release). For these reasons, a key component of the current studies will be to assess these parameters via nasal biopsies. These studies will be used to explore: 1. the extent of viral infection – i.e. whether this occurs diffusely throughout the nares or remains focally within the adenoids; 2. the comprehensiveness of epithelial infection at each site 3. the presence and extent of infection-associated cell death and 4. whether this represents cytopathic (necrotic) or apoptotic cell death.
4. We will also determine whether RV infection in the asthma cohort is associated with increased use of rescue inhaler and decreased lung function. Use of albuterol metered dose inhaler will be assessed by diary and decreased FEV1 monitored by a Microlife hand held monitor

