## 1.3. Clinical Studies

Approximately 2000 volunteers have been challenged in studies conducted by [name], [name], [name], [name], and our other colleagues at UVA over the last 30 years and no serious complications attributable to the viral infection have been detected. The clinical syndrome associated with experimental infection is well-described. Challenge of volunteers with 100 TCID50 produces infection in 90-95% of susceptible volunteers. Symptoms first appear within 24 hours after inoculation and peak at 48-72 hours after challenge. The clinical syndrome is comparable to that reported in natural colds (52, 53) although in one study with identical definitions for duration, the median duration of illness was 3.5 days in volunteers with experimental colds and 5.5 days in volunteers with natural colds (54). Approximately 1/3rd of RV infections, whether natural or experimental, are asymptomatic. Virus shedding in infected volunteers follows a pattern similar to that of the symptoms. Virus concentrations in nasal lavage fluid, based on titers in culture, generally peak 2-3 days after challenge and then rapidly decrease. Virus can still be recovered by culture in 20% of subjects on day 18 after challenge, but no virus shedding is detected by day 20 (55). To the best of our knowledge, human RV-16 has not been withdrawn from investigation or marketing in any country for any reason related to safety or effectiveness. In our studies, we have observed neutropenia in most of the 29 asthmatic subjects and also 16 controls following inoculation with RV-16 in our experimental challenges, which we believe is in keeping with the recruitment of neutrophils into the airways stimulated by RV. However, except for the possibility of bronchitis, which occurs infrequently in experimental infections, no subject has developed clinically significant bacterial infections in our studies, including bacterial sinusitis. Additionally, no subject in our studies with RV-16 has developed ANC's <1000 cells/mm^3.

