### **Study Visit 2 - Inoculation (Day 0)**

1. Urine pregnancy test for all women of childbearing potential.
2. Vital Signs (blood pressure, heart rate, temperature, height, weight)
3. Prior to inoculation asthma control will be confirmed by the following means -
  - a. Diary cards will be reviewed
  - b. AEs review
  - c. Spirometry – Must demonstrate normal lung function (FEV1 > 70% predicted or FEV1/FVC ratio > 75% for subjects with FVC values between 80 and 87% predicted whose FEV1 values fall below 70%).
  - d. A limited physical examination will be performed including chest auscultation
4. Nasal scraping
5. Nasal wash / sponge

6. Blood draw – 50mls of blood will be obtained for PBMCs ONLY if not collected at Visit 1
7. Exhaled nitric oxide (FeNO) on asthmatics only
8. Inoculation of subjects with RV-16

Continued eligibility must be confirmed during the initial part of this study visit. Sample collection and the inoculation may be delayed if a subject is ill or has evidence of loss of asthma control. The inoculation will not occur if the upper airway modified Jackson criteria symptom scores are  $\geq 7$ . The participant may be brought back to continue the Day 0 visit. Procedures completed may be repeated to confirm the subject's eligibility. The repeat visit must occur within the stated visit window from Visit 1.

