***Analysis of albuterol metered dose inhaler utilization:*** Albuterol metered dose inhaler utilization will be evaluated on challenge days 0, 1, 2, 3, 4, and 7 within the asthma cohort to determine if the frequency of albuterol inhaler utilization is related to severity of symptoms.

**Analytical approach:** Based on diary records, the total number of times that the subjects used their albuterol metered dose inhaler will be determined for study days 0, 1, 2, 3, 4, and 7, and these frequencies will be analyzed via a Negative Binomial generalized estimating equation (GEE) model. **Hypothesis testing:** Our primary interest, will be to compare albuterol metered dose inhaler utilization on post-challenge days 3 and 4 when lower and upper respiratory symptoms are expected to peak to challenge days 0, 1, 2, and 7. The Wald test will be the pivotal quantity for the *inter-day* comparisons and the multiple comparison experimental type 1 error rate for the inter-day comparisons will 0.05.

**Secondary analyses:** As secondary analyses, Negative Binomial GEE regression models will be utilized to determine if RV loads and total upper and lower respiratory symptoms scores on challenge days 0, 1, 2, 3, 4, and 7 predict albuterol metered dose inhaler utilization on challenge days 0, 1, 2, 3, 4, and 7.

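### The albuterol test does not isolate the before-versus-after-inoculation contrast that exploratory outcome 4 asks about, so a sustained increase in use is diluted or penalised

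*Combined protocol and SAP*

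**What the plan says.** Section 3.3 (Exploratory Outcomes), item 4, states: "We will also determine whether RV infection in the asthma cohort is associated with increased use of rescue inhaler and decreased lung function". Albuterol use comes from the diary.

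The analysis is in section 13.4.4, for the asthma cohort only. Its stated aim is different: "to determine if the frequency of albuterol inhaler utilization is related to severity of symptoms". Daily frequencies for days 0, 1, 2, 3, 4 and 7 enter a negative binomial GEE. The main interest is "to compare albuterol metered dose inhaler utilization on post-challenge days 3 and 4 when lower and upper respiratory symptoms are expected to peak", and the comparison days follow in the same sentence: "respiratory symptoms are expected to peak to challenge days 0, 1, 2, and 7". On error control it says only that the "multiple comparison experimental type 1 error rate for the inter-day comparisons will 0.05". It names no correction, and does not say whether the reference days are pooled or taken one at a time.

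Inoculation is on day 0 (section 3.1). Section 1.3 gives the time course: "Symptoms first appear within 24 hours after inoculation and peak at 48-72 hours after challenge".

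Three other places bear on the point:
- FEV1, the other half of item 4, is analysed in section 13.4.4 as change from day 0.
- Section 13.6 defines a before-versus-after null hypothesis, but only for primary and secondary outcomes.
- Section 13.4.5 says that most exploratory endpoints will be described rather than tested.

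**The concern.** The question and the test do not match. Whether infection raises rescue use is answered by comparing use after inoculation with use before it. In the written test, day 0 is the only reference day not preceded by inoculation. Days 1 and 2 fall after symptom onset, day 2 lies at the start of the stated symptom peak, and day 7 is still within the monitored illness.

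If rescue use rises on day 1 and stays up, most of the written comparison sets infected days against infected days. The trial could then report little difference between days and leave the reader unsure whether use rose at all. The analysis has no control-group comparison to fall back on, and nothing tells the analyst that the day-0 contrasts are the ones that answer item 4.

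**Working it through.** The plan gives no expected use rate, effect size or power for albuterol, so there is no figure of its own to reproduce.

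**Inputs from the documents.** 20 asthmatics (section 3.1); index days 3 and 4; reference days 0, 1, 2 and 7; an overall inter-day error rate of 0.05 (section 13.4.4).

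**1. Reference days pooled, sustained increase.** Let use be multiplied by RR on every day after inoculation. The log-scale contrast is the mean of days 3 and 4 minus the mean of days 0, 1, 2 and 7:

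log RR − (0 + 3 log RR)/4 = (1/4) log RR, so the ratio seen is RR^(1/4).

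| True RR | Ratio seen, log-scale pooling | Ratio seen, RR / [(1 + 3RR)/4] | Days 3–4 vs day 0 |
|---|---|---|---|
| 1.5 | 1.11 | 1.09 | 1.5 |
| 2 | 1.19 | 1.14 | 2 |
| 3 | 1.32 | 1.20 | 3 |

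**2. Days compared in pairs, sustained increase.** There are 2 × 4 = 8 contrasts. The 2 × 3 = 6 against days 1, 2 and 7 have an expected ratio of RR/RR = 1. The two against day 0 keep the full RR. With Bonferroni (assumed), each is tested at 0.05/8 = 0.00625.

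Steps 1 and 2 do not depend on any assumed use rate.

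**3. Illustrative power, sustained doubling.** Assumptions: day-0 mean of 0.5, 1 or 2 uses a day, between-subject variance 0.8, day-level dispersion 0.3, robust Wald tests, about 3,000 simulated trials per setting.

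| Test | 0.5/day | 1/day | 2/day |
|---|---|---|---|
| Pooled contrast at 0.05 | 17% | 21% | 25% |
| At least one day-0 pair at 0.00625 | 28% | 44% | 61% |
| Days 3–4 vs day 0, single test at 0.05 | 44% | 63% | 78% |
| Pooled contrast at 0.05, no true effect | 8% | 9% | 10% |

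With 20 subjects the unadjusted robust Wald test rejects too often when there is no effect (8–10% for both 0.05-level tests), so the power figures are somewhat optimistic. Lower rates may be more realistic, because entry requires controlled asthma and excludes β2-agonist use on 4 or more days in any week. In separate simulations with 20 subjects and gamma shape 0.8, at 0.3 uses a day, at least one day-0 pair was positive in 18–22% of trials for a doubling. At 0.15 a day it was 3–5%.

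**4. A peaked course.** Assume multipliers of 1.2, 2.5, 3, 3, 2, 1.5 and 1.2 on days 1 to 7. Day 3 or 4 against day 1 or day 7 is then 3/1.2 = 2.5, and against day 2 it is 3/2.5 = 1.2. The pooled log-scale ratio is 3/(1 × 1.2 × 2.5 × 1.2)^(1/4) = 3/3.6^(1/4) = 2.18, against 3 for day 0 alone. At 0.3 uses a day, any of the eight pairs was positive in 77% of simulated trials, and at least one infected-day pair in 66%.

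**The case against.** The strongest reply is that day 0 is one of the reference days. A reader might infer that a sustained increase would show as no effect and that the trial would wrongly conclude that infection did not raise rescue use. The documents do not support that. The day-0 pairs keep the full ratio, a pooled contrast keeps a quarter of the log effect, and the plan attaches no decision rule to this outcome.

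Second, the documents mostly describe a peak, not a plateau. Section 1.3 puts it at 48–72 hours, section 13.4.4 expects it on days 3 and 4, and section 5.1 reports more frequent albuterol use during peak symptoms in some earlier asthmatics. Step 4 shows that such a course is much less affected. This stands, and it limits the size of the point.

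Third, the day 3–4 contrast suits the aim stated in section 13.4.4, and the same section plans regressions of albuterol use on RV load and symptom scores. These are useful support. They estimate a gradient with load or symptoms, though, and do not test whether use rises after inoculation.

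Fourth, a reader might infer that a run-in baseline would bring a very large gain in power. At 0.3 uses a day and a sustained doubling, a run-in versus days 1–7 test was positive in about 86% of simulated trials at 0.05. The same test falls to 44% at 0.00625, so a comparison with the pairwise tests mixes error rates, test types and amounts of data. The run-in is also a doubtful sole baseline: section 8.2 has cards completed weekly before inoculation, while sections 5.1 and 8.2 have daily recording afterwards. That change alone could look like an increase.

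Last, a reader might infer that selecting day 0 for good control hides an effect. Section 8.2 (Visit 2) does say "Sample collection and the inoculation may be delayed if a subject is ill or has evidence of loss of asthma control". A low day-0 rate, however, makes an increase easier to show, not harder.

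**Conclusion.** The mismatch is real and follows from the text: item 4 needs a before-versus-after contrast, and section 13.4.4 does not single one out. A sustained increase is cut to a quarter of its log size if reference days are pooled (2 appears as about 1.19). In pairwise testing it is null in six of eight contrasts and carries a multiplicity penalty in the other two. It is weakened, not erased.

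The dilution and the count of contrasts assume a flat increase over days 1 to 7; a peaked course is less affected. The 0.00625 threshold assumes Bonferroni. Every power figure rests on assumed use rates and dispersion. Because the outcome is exploratory, this is a low-priority clarification that costs little.

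**What to change.** In section 13.4.4:
- Name one contrast within the asthma cohort, from the planned negative binomial GEE, as the test of item 4: post-inoculation use versus day 0, two-sided 0.05. Choose the post-inoculation period in advance, either days 3–4 or all diary days 1–7, including days 5 and 6, which the present analysis leaves out.
- Keep days 3–4 versus days 1, 2 and 7 as a descriptive analysis of timing, and say whether reference days are pooled.
- Leave out of the count any albuterol given to reverse a methacholine challenge. A challenge falls on day 4, an index day.
- Use the run-in diary (Visit 1 to inoculation, with log number of days as offset) as an added baseline or sensitivity analysis, but only if the run-in cards record puff counts comparably to the later cards.

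The cost is a few lines of analysis text, entry of diary data for days 5 and 6 if that period is chosen, and entry of run-in counts if they prove usable. The downside is that day 0 is a single day, so precision is limited. Because inoculation may be deferred when control is poor, day 0 may also be a better-than-usual day, which would flatter the increase; a usable run-in would help to check this.

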### 3.4. Stratification, Randomization, and Blinding/Masking

N/A. This is an open label study of a single RV inoculation. Data will be compared between healthy controls, allergic rhinitic controls, and asthmatic subjects.

#### 3.4.1. Procedure for Unblinding/Unmasking

N/A. Study is not blinded.

## 4. Selection of Participants and Clinical Sites/Laboratories

### 4.1. Rationale for Study Population

Asthmatics will be studied as the relevant target for RV-induced asthma exacerbations and compared to control and AR subjects to identify the basis for their unique sensitivity. We will study mild asthmatics who are well-controlled with or without long-term controllers and low risk insofar as they have no recent (3-year) history of exacerbations to mitigate the risk of a severe asthma exacerbation during the study. It is our contention that it is the innate response to RV-infected *nasal* epithelium that is the relevant target of inquiry and, as such, **that AR subjects will behave identically to asthmatics**, however, in their case, the absence of relevant addressins and chemotaxins in their lungs precludes development of a lower airway response. We will therefore also enroll AR subjects to validate this concept that both asthmatic and AR cohorts will display increased circulating mediators of inflammation, but that only in asthmatics will

this translate to increased lower airway inflammation. Results will be evaluated in comparison to a non-allergic non-asthmatic control cohort and we will consider the potential impact of asthma long-term controllers regarding modulation of measures of airway mediators and markers of inflammation.

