#### 4.3. Exclusion Criteria (all subjects)

Individuals who meet any of these criteria are not eligible for enrollment as study participants:

1. Positive test for serum neutralizing antibody to RV16 at enrollment visit ( $\geq 1:8$ )(Visit 1).

2. Upper airway modified Jackson criteria symptom scores  $\geq 7$  at time of inoculation.
3. Chronic heart disease including bradycardia, lung diseases other than asthma, or other chronic illnesses including epilepsy, peptic ulcer disease, thyroid disease, urinary tract obstruction, vagotonia, autoimmune disease, primary or secondary immunodeficiency or any household contacts who are known to be immune deficient. Any medical conditions that could be adversely affected by the administration of cholinergic agent.
4. Any use of nasal corticosteroids, LT modifiers, omalizumab, within 4 weeks prior to Visit 1.
5. Current use of  $\beta$ -blockers or cholinesterase inhibitors (for myasthenia gravis)
6.  $\beta 2$ -agonist use  $\geq 4$  days/week in any week or  $\geq 2$  nights during the month before Visit 1.
7. Recent (within 3-yr) asthma exacerbation requiring urgent care visit (unless the treatment involved only the use of a bronchodilator), hospitalization, or oral CCS
8. Intubation or management in the ICU for an asthma exacerbation ever.
9. An upper or lower respiratory tract infection within 2 months prior to enrollment.
10. Previous nasal or sinus surgery within the last 12 months
11.  $>5$  pack-year smoking history or any smoking within the past 6 mos.
12. Hemoglobin  $<11.5$  g/dL for non-African American subjects or hemoglobin  $< 11.0$  g/dL for African American subjects detected at Visit 1.
13. Laboratory values (other than hemoglobin and ANC) measured at Visit 1 that are considered to be of clinical relevance by the Investigator.
14. Absolute neutrophil count (ANC)  $<1500$  cells/mm^3 (or 1.5 K/ $\mu$ L) or absolute lymphocyte count (ALC)  $<800$  cells/mm^3 detected at Visit 1.
15. Use of investigational drugs within 12 weeks of participation
16. Past or current medical problems or findings from physical examination or laboratory testing that are not listed above, which, in the opinion of the investigator, may pose additional risks from participation in the study, may interfere with the participant's ability to comply with study requirements or that may impact the quality or interpretation of the data obtained from the study.

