All subjects in the proposed study will be inoculated with RV-16 and monitored daily for 4 days following inoculation in the clinical research center at UVA hospital and again on day 7 dpi. Daily monitoring will include upper and lower respiratory symptoms scores, and FEV1 measurements (using a hand held FEV1 monitor given to each subject), which will be recorded twice daily (morning and evening) on diary cards. Subjects will also be recording the number of puffs of albuterol used daily from metered dose inhalers. In addition, monitoring each morning will include a physical examination focused on the respiratory tract, along with spirometry and measurements of expired nitric oxide (FeNO). This monitoring will be done to enhance our ability to detect changes during the acute infection and to ensure safety. The research team member will be a licensed physician or nurse and will be readily available should any problems occur. Thus far, no significant problems or serious adverse events have occurred for any of the asthmatics inoculated with either RV-16 or RV-39. The inclusion of mild-/moderate-persistent asthmatics who are very well controlled on inhaled CCS could lead to more severe exacerbations. However, this has not been the experience of other research groups enrolling this population (58). Furthermore, as noted, the average American has 4 respiratory infections/yr and we would argue that as none of these subjects will have had even a modest asthma exacerbation in the previous 3 years (over which time they will on average have had 12 RV infections) we do not feel this modification adds an untoward risk to the study. And that the current safety monitoring criteria will continue to suffice.

As for any adverse long-term safety effects of an experimental RV-16 infection, the cold symptoms observed have been generally similar to, but a bit shorter in duration than a natural RV infection (see above). Because most adults will

experience at least one or two viral induced colds a year, it would be very difficult to differentiate any adverse effects of an RV-16 experimental infection from the effects of a subsequent natural respiratory tract infection in an effort to evaluate any safety problems long-term.

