## **5.2. Risks of Investigational Product or Intervention cited in Medical Literature**

Recently, in European studies, challenges with RV-16 were well-tolerated by subjects with moderately severe asthma who were treated with inhaled corticosteroids (9, 59) . However, asthmatic subjects in those studies were using inhaled steroids at the time of inoculation, which would interfere with our goals of judging the effects of RV infection on lower respiratory tract symptoms and bio-markers of inflammation.

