### **7.3. Prohibited Medications**

Topical (nasal or inhaled) corticosteroids (CCS), oral corticosteroids, leukotriene modifiers, antihistamines, omalizumab, theophylline, short- and long-acting anti-muscarinic agents (LAMAs), long-acting  $\beta$ -agonists (LABAs), cromolyn, and nedocromil.

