### 11.2. Participant Stopping Rules and Withdrawal Criteria

Participants may be prematurely terminated from the study for the following reasons:

1. The participant elects to withdraw consent from all future study activities, including follow-up.
2. The participant is "lost to follow-up" (i.e., no further follow-up is possible because attempts to reestablish contact with the participant have failed).
3. The participant dies.
4. The Investigator no longer believes participation is in the best interest of the participant.
5. Individual safety stopping rules:
  - a. The participant develops a medical condition or is started on new medication(s) that, in the opinion of the investigator, may pose additional risks from participation in the study, may interfere with the participant's ability to comply with study requirements or that may impact the quality of the data obtained from the study.
  - b. A severe asthma exacerbation that requires treatment in the emergency room, hospitalization, or the use of systemic steroids, at any time during the study.
  - c. Use of a required but excluded medication such as inhaled corticosteroids or leukotriene modifiers.
  - d. Non-adherence to study procedures. Patients who miss visit 3 or 4 may be permitted to remain in the study as long as they comply with all other visits.
  - e. Pregnancy
  - f. Positive CoVID-19 test

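### Asthmatics on inhaled steroids are included by sections 4.1 and 5.1 but are on a prohibited drug under 7.3, and no analysis uses controller status

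*Combined protocol and SAP*

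**What the plan says.** **Sections that include controller users.** Section 4.1: "We will study mild asthmatics who are well-controlled with or without long-term controllers". Section 5.1 cites experience with asthmatics controlled on inhaled corticosteroids with or without long-acting beta-agonists. It then treats their inclusion here as a change to be defended: "The inclusion of mild-/moderate-persistent asthmatics who are very well controlled on inhaled CCS could lead to more severe exacerbations". The asthma inclusion criteria in 4.2 do not mention controllers. Exclusion 4 in 4.3 reads "Any use of nasal corticosteroids, LT modifiers, omalizumab, within 4 weeks prior to Visit 1" and names neither inhaled steroids nor long-acting beta-agonists.

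**Sections that exclude them.** Section 7.3 prohibits "Topical (nasal or inhaled) corticosteroids (CCS), oral corticosteroids, leukotriene modifiers, antihistamines, omalizumab, theophylline", and the list goes on to long-acting beta-agonists and other controllers, with no exception for stable use. Section 11.2, item 5c, gives as a possible reason for termination: "Use of a required but excluded medication such as inhaled corticosteroids or leukotriene modifiers". Section 5.2 sets this study apart from European challenges in subjects taking inhaled steroids, "which would interfere with our goals of judging the effects of RV infection on lower respiratory tract symptoms and bio-markers of inflammation".

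**Analysis.** Section 4.1 promises to consider the impact of controllers on airway mediators and inflammation markers. Section 13.4.1 names three populations, with asthma undivided.

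**Safety rationale.** Section 5.1 supports the inclusion by noting that these subjects will have had no exacerbation in 3 years, "over which time they will on average have had 12 RV infections".

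**The concern.** The documents give two answers on whether a well-controlled asthmatic taking an inhaled steroid belongs in the study. The answer decides who is inoculated and who is retained.

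It also decides what the asthma cohort represents. Section 4.2 requires AR subjects to have used no asthma controllers for 6 years, and healthy controls are non-asthmatic. Controller treatment can therefore occur only in the asthma cohort, where it is confounded with the group contrast. If the treatment suppresses the lower-airway response, as 5.2 implies, a small or absent asthma effect on symptoms could reflect either biology or treatment. The planned models would not tell these apart.

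**Working it through.** **Step 1: follow one subject through the text.** Take an asthmatic with an ACT score of at least 20 and normal lung function who takes a stable inhaled steroid.

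| Section | Consequence |
|---|---|
| 4.1, 5.1 | Belongs to the intended population |
| 4.2, 4.3 item 4 | No criterion bars the drug |
| 7.3 | On a prohibited drug |
| 11.2(5c) | May be terminated |
| 11.3 | Replaced if withdrawn |
| 5.2 | Drug said to interfere with study goals |

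No sentence ranks these sections or gives a washout.

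**Step 2: look for controller status in section 13.**
- IL-25: group, day and the day-0 value.
- Lower respiratory symptoms: group and challenge period, or group and day.
- RV load: group and day.
- FeNO: group, day and baseline. PD20 and eosinophil count: group.

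There is no controller covariate, stratum, subgroup or sensitivity analysis, so the promise in 4.1 has no method behind it.

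**Step 3: which endpoints are exposed.** Section 5.2 names lower respiratory symptoms and inflammation biomarkers. These correspond to primary endpoint 2 and secondary endpoint 4 (eosinophil count, FeNO, PD20). Primary endpoints 1 and 3 are nasal, and no section says that inhaled controllers change them.

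**Step 4: reproduce the plan's power figures.** Section 13.7 uses a two-sample t-test with 20 per group, two-sided alpha 0.05/3 and power 0.80.
- Aim 1, SD 0.12: detectable factor 1.136 (stated 1.14).
- Aim 2, SD 1.32: detectable factor 25.4 (stated 25). Power at exactly 25 is 0.796.

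Both reproduce. In SD units the Aim 2 difference is log10(25)/1.32 = 1.398/1.32 = 1.059.

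**Step 5: illustration only.** Let a share f of the asthmatics be treated, and let treatment remove a proportion b of their difference from the comparison group. The expected difference is multiplied by (1 − f·b). Power comes from the noncentral t with noncentrality D·√(n/2), n = 20, at the same alpha. Both f and b are assumptions, because the documents give neither.

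| f | b | 1 − f·b | D (SD) | Power |
|---|---|---|---|---|
| 0 | – | 1 | 1.059 | 0.80 |
| 0.10 | 0.25 | 0.975 | 1.033 | 0.77 |
| 0.25 | 0.50 | 0.875 | 0.927 | 0.67 |
| 0.50 | 0.50 | 0.750 | 0.794 | 0.51 |
| 0.50 | 1.00 | 0.500 | 0.530 | 0.22 |

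Allowing for the wider spread of a mixed cohort lowers these rows by at most about 0.03. The 1.06 SD scale is borrowed from the RV load calculation, because 13.7 has no power calculation for lower respiratory symptoms. The table shows how dilution acts. It does not forecast power for any endpoint.

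**Step 6: the infection count.** Section 5.1 starts from 4 respiratory infections a year, with no cause specified: 4 × 3 = 12. The product is then called rhinovirus infections. The next paragraph says most adults have at least one or two viral colds a year, which over 3 years is at least 3 to 6 and again not all rhinovirus.

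**The case against.** Several limits on the point stand.

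- **Withdrawal is permissive.** Section 11.2 says participants may be terminated. Item 5c can be read as drugs that become necessary on study, and Appendix 1 itself starts inhaled steroids for certain FEV1 falls. A reader might infer that every eligible steroid user must be withdrawn, but the text does not say so. The firm conflict is with 7.3.
- **Exclusion 6 may catch some users.** It limits frequent beta-2-agonist use without saying whether long-acting products count. If they do, regular users of those products are already excluded. Inhaled-steroid users are not affected.
- **The two consequences are alternatives.** If 7.3 is enforced, treated asthmatics are withdrawn and replaced, and nothing is diluted. If 4.1 and 5.1 are followed, cohorts are pooled but the cycle of inoculation and withdrawal does not arise.
- **Not every asthma result is compromised.** A reader might infer that any null asthma result would be uninterpretable. The documents do not support that. Nasal steroids are excluded for 4 weeks before Visit 1, 5.2 does not mention nasal IL-25 or viral load, and AR-versus-control contrasts are untouched. For the nasal response, 4.1 predicts that AR and asthma will look alike.
- **The infection count is a floor.** A reader might conclude that the true figure is 3 to 6, but the text says at least one or two colds a year. What stands is the relabelling of infections of any cause as rhinovirus. The safety case also rests on the absence of exacerbations, other groups' experience and the monitoring plan.

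None of this removes the unqualified prohibition in 7.3 or supplies the missing analysis.

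**Conclusion.** The contradiction is real, and nothing in the documents resolves it. It bears on who is inoculated and retained and, if treated asthmatics are kept, on what the asthma contrast for primary endpoint 2 and the secondary inflammation markers can show. That makes it more than a missing detail.

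The size is unknown. The power range of 0.77 to 0.22 rests wholly on assumed shares and blunting, and on an effect size taken from an endpoint with no documented blunting. It should not be quoted as the trial's expected power loss. No view is taken here on which medication rule is right.

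**What to change.** 1. Reconcile 4.1, 4.3 item 4, 5.1, 5.2, 7.3 and 11.2(5c) into one statement on controllers that governs eligibility, prohibited drugs and withdrawal. Say whether exclusion 6 covers long-acting beta-agonists and whether 5c covers baseline use. The choice of rule is the sponsor's.
2. If any controller-treated asthmatic is or has been enrolled, record controller status at Visit 1. Pre-specify a sensitivity analysis of the asthma contrasts restricted to controller-free asthmatics, for lower respiratory symptoms, FeNO, eosinophil count and PD20. Section 8 schedules FeNO for asthmatics only, so there the check would be on the change within the cohort. Report the two nasal primary endpoints the same way, as supportive.
3. Correct the infection figure in 5.1 so that infections of any cause are not called rhinovirus infections.

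The cost is amendment wording, one recorded variable and one added analysis. The downside is precision. If, say, 10 of the 20 asthmatics are controller-free, the standard error of a mean contrast against 20 comparators rises by a factor of √[(1/10 + 1/20)/(1/20 + 1/20)] = √1.5 = 1.22, assuming a common SD. The restricted estimate therefore checks consistency and does not replace the main analysis.
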